#### IP Exposure Period in 271 in Months

If a subject's last dose regimen is Q2W, then

IP Exposure Period = {[min(EOIP date + 14 days, EOS date) - First Dose Date +1]/365.25}\*12.

If a subject's last dose regimen is QM, then

IP Exposure Period =  ${[min(EOIP date + 28 days, EOS date) - First Dose Date +1]/365.25}*12.$ 

## Non-HDL-C

Non-HDL-C =Total cholesterol - HDL-C

#### **Treatment Emergent Adverse Events**

Events are categorized as Adverse Events (AEs) starting on or after first dose of investigational product as determined by the flag indicating if the value of the Adverse Events eCRF question "Did event start before first dose of investigational product?" is No or missing and up to including 30 days after the end of investigational product or the End of Study date, whichever is earlier.

## Study Exposure Period in Months

For each subject enrolled into the extension study,

Study Exposure Period = (EOS date – study day 1 + 1) /365.25 \*12

## Study Cohorts

#### All tables will be summarized by the following study cohorts:

- Non-Apheresis at Baseline
- Apheresis at Baseline

Statistical Analysis Plan: 20110271

Dated: 26 May 2018 Page 13 of 27

# 7. Analysis Subsets

#### 7.1 Primary Analysis Set

 The evaluable analysis set (EAS) for the final analysis includes all subjects enrolled in this study. This analysis set will be used in all the analyses unless otherwise specified.

- HoFH Analysis Set (HAS): all subjects who received at least 1 dose of evolocumab in Study 20110271 and either met clinical criteria of HoFH or who had supportive genetic information
  - Evolocumab Titration Analysis Set (TAS): subjects who were exposed to evolocumab 420 mg QM for at least 12 weeks in Study 20110271 and then to evolocumab 420 mg Q2W for at least 12 weeks in Study 20110271 (all subjects in this analysis set had HoFH)
  - Adolescent subgroup: all adolescent subjects (ages 12 to < 18 years) who received at least 1 dose of evolocumab in Study 20110271 (all adolescent subjects had HoFH)
- Responder Analysis Set (RAS): subjects included in the Interim Analysis Set (IAS) who had UC LDL-C reduction >=15% at any time during study 20110233.
   This analysis set is only for the interim analysis but not for the final analysis.
- LDL Receptor Defective Analysis Set (RDAS): all LDL receptor defective subjects who received at least 1 dose of IP in study 20110233. This analysis set is only for the interim analysis but not for the final analysis.
- Severe FH Analysis Set (SAS): all subjects who received at least 1 dose of evolocumab in Study 20110271 and were not included in the HoFH Analysis Set

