2.2.4.3 Phase 2 Interim Efficacy Analysis Results for the Randomized, Controlled, Open-label Extension

Interim results of this open-label extension study show that treatment with AMG 145 was effective in reducing LDL-C concentrations in all subjects who had not previously received AMG 145, regardless of whether or not they had received other lipid lowering therapies (Figure 2). Subjects who received AMG 145 in their parent study maintained their LDL-C reductions in the extension study at levels similar to that in the parent study. Furthermore, results demonstrate reversibility of the treatment effects of AMG 145. Subjects who had previously received AMG 145 in their parent study and who were randomized to standard of care in the extension study (ie, discontinued AMG 145 therapy), saw their LDL-C concentrations rise to that of subjects who had never received AMG 145 (ie, standard of care alone) by week 4 in the extension.

Figure 2. Aggregate Interim Analysis Percent Change From Baseline in Calculated LDL-C in Subjects Transitioning From AMG 145 (Q2W or Q4W) or Placebo to AMG 145 and Standard of Care or Standard of Care Alone

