8. REMOVAL AND REPLACEMENT OF SUBJECTS

8.1 Removal of Subjects

Subjects have the right to withdraw fully or partially from the study at any time and for any reason without prejudice to his or her future medical care by the physician or at the institution.

Withdrawal of full consent for a study means that the subject does not wish to receive further investigational treatment and does not wish to or is unable to continue further study participation including any follow-up in person, by phone, through 3rd parties including relatives or friends, via discussion with other treating physicians, and by use of medical records; subject data up to withdrawal of full consent will be included in the analysis of the study. Any subject may withdraw full consent to participate in the study at any time during the study. The investigator will discuss with the subject appropriate procedures for withdrawal from the study. The investigator should ask the subject's consent to perform the procedures listed under the final study visit.

Subjects may decline to continue receiving IP or other protocol-required procedures at any time during the study. If this occurs, the investigator will discuss with the subject appropriate procedures for discontinuation from IP or other protocol-required procedures and should encourage the subject to continue with collection of data, including endpoints and adverse events. These subjects, as well as those who have stopped receiving IP or other protocol-required procedures for other reasons (eg, investigator or sponsor concern) should continue the schedule of study observations. If the subject is unable or

unwilling to continue the schedule of observation, the investigators should clarify what type of follow-up the subject is agreeable to: in person, by phone/mail, through family/friends, in correspondence/communication with other physicians, and/or from review of the medical records.

Should a subject (or a legally acceptable representative) request or decide to withdraw from the study, all efforts will be made to complete and report the observations as thoroughly as possible up to the date of withdrawal. All information should be reported on the applicable eCRFs.

Reasons for removal from protocol-required investigational product might include:

- withdrawal of full consent
- subject request to end investigational product administration
- administrative decision by Amgen
- decision by the primary investigator / physician

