# 2.2 Secondary

 To characterize the efficacy of long-term administration of AMG 145 as assessed by low density lipoprotein cholesterol (LDL-C) and non-high-density lipoprotein cholesterol (non-HDL-C), lipoprotein(a) [Lp(a)], apolipoprotein B (ApoB), total cholesterol/HDL-C ratio, ApoB/Apolipoprotein A-1 (ApoA1) ratio, and response of LDL-C reduction (15% or greater) in subjects with severe familial hypercholesterolemia

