# 10.6 Analyses of Secondary and Exploratory Endpoints

# 10.6.1 Analyses of Secondary Endpoints

Descriptive statistics on all endpoints at all scheduled visits and time points will be provided by apheresis status at study entry and by visit including percent change from baseline in the following lipid parameters:

- LDL-C
- non-HDL-C
- Lp(a)
- ApoB
- total cholesterol/HDL-C ratio
- ApoB/ApoA1 ratio
- Number and percent of patients with LDL-C reduction of 15% or greater from baseline by visits will also be provided.

For continuous endpoints, descriptive summaries including group means will be displayed. For response rate analysis, number and percent of responders at each visit will be displayed. All analyses will be performed for the HoFH and severe FH analysis sets unless specified.

Depending on subject's apheresis status, protocol-specified visits vary.

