# Appendix A. Analytical Study Week Assignments

Selected endpoints will be summarized by scheduled study visits in descriptive analyses. Since the actual visits may not exactly coincide with their scheduled visit day, the actual visit day is mapped to the study visit generally by non-overlapping consecutive intervals covering the entire time continuum, with scheduled visit time being the center of each interval. The mapping intervals for all distinct schedules are summarized in the following table.

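### The by-visit lipid tables pool values taken on and after AMG 145, so they cannot separate a change in drug effect over 260 weeks from stopping the drug

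*SAP*

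**What the plan says.** The secondary objective (SAP 2.2) begins "To characterize the efficacy of long-term administration of AMG 145". It does not say whether efficacy is meant while taking the drug or regardless of stopping.

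SAP 10.6.1 serves that objective: "Descriptive statistics on all endpoints at all scheduled visits and time points will be provided by apheresis status at study entry". On the sets it says "All analyses will be performed for the HoFH and severe FH analysis sets unless specified". SAP 7.1 defines the severe FH set as "all subjects who received at least 1 dose of evolocumab in Study 20110271 and were not included in the HoFH Analysis Set"; the HoFH set also needs one dose. Those definitions admit the subject once and for all. Which of the subject's values count is settled in 10.6.1 and Appendix A. In Appendix A "the actual visit day is mapped to the study visit generally by non-overlapping consecutive intervals covering the entire time continuum", and where a window holds several records the choice goes by distance from the target day, or by apheresis day for apheresis patients. Dosing status plays no part.

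Protocol 8.1 covers subjects who decline further IP and those who have stopped it for other reasons; its text reads "eg, investigator or sponsor concern) should continue the schedule of study observations". Lipid panels belong to the quarterly visits (Protocol 7.1.2.5).

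Protocol 2.2.4.3 describes the phase 2 extension: subjects who had AMG 145 in the parent study and were then randomised to standard of care "saw their LDL-C concentrations rise to that of subjects who had never received AMG 145 (ie, standard of care alone) by week 4" of the extension.

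The SAP does limit exposure time elsewhere. Section 6.3 closes the treatment-emergent adverse event window 30 days after the end of IP, or at end of study if earlier. It ends IP exposure 14 days (Q2W) or 28 days (QM) after the last dose, capped at end of study. Neither limit is applied to lipids.

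**The concern.** The study is single-arm and runs 260 weeks, and durability of LDL-C lowering is a natural question to put to it. If the mean reduction or the 15% response rate at late visits is lower than at early ones, two explanations compete: the drug does less in people still taking it, or more of the values come from people who have stopped. The planned tables mix both kinds of value in one mean and do not show how many there are of each. Because the protocol's own phase 2 data indicate that the effect is reversible, the distinction matters for what the secondary results can be said to show. The optional sensitivity analyses in SAP 9.4 concern the primary endpoint, which is adverse events, so they do not fill the gap.

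**Working it through.** The plan gives no figure on this point. Its only sample-size figure is the precision table for adverse event incidence (Protocol 10.2, SAP 3.2). It reproduces with a Wald interval (16/310: 0.0516 ± 1.96 × √(0.0516 × 0.9484/310) = 0.027 to 0.076, stated as 0.03 to 0.08) and has no bearing here.

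**Step 1: trace one off-drug value.** From week 36 the lipid window for week n runs from day (n-6)×7+1 to day (n+6)×7, which is 84 days. Take a hypothetical QM subject whose last dose is on day 400 and who stays on schedule. The week 72 panel is due on day 505, inside the window 463 to 546, and is 105 days after the last dose. It enters the week 72 mean like any other value, and so do all later panels.

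**Step 2: dilution.** Let f be the share of values at a visit taken off IP. The visit mean is (1-f)×E_on + f×E_off. The documents do not give f, so a range is assumed. E_on is set to an assumed -20%, and separately to -55.99%, the placebo-adjusted week 12 figure for 420 mg Q4W in Protocol Table 2. E_off = 0 is full reversal. The response column assumes 60% on drug and none off drug.

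| f | E_on = -20%, full reversal | E_on = -20%, half the effect kept | E_on = -55.99%, full reversal | Response (60% on drug) |
|---|---|---|---|---|
| 5% | -19.0 | -19.5 | -53.2 | 57% |
| 10% | -18.0 | -19.0 | -50.4 | 54% |
| 20% | -16.0 | -18.0 | -44.8 | 48% |

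Under full reversal the shift is f times the on-drug effect: 1, 2 and 4 points in the second column; 2.8, 5.6 and 11.2 points in the fourth.

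**Step 3: the opposing effect.** Subjects with less than 5% LDL-C reduction may be withdrawn from the study at week 12 or 24 (Protocol 6.1.1), and nothing is imputed (SAP 9.3.2). If a share g of the cohort with mean change 0 leaves, a full-cohort mean E becomes E/(1-g) among those who remain. For E = -20% and g = 5%, 10%, 20% this gives -21.1, -22.2 and -25.0.

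**Step 4: both together.** If stopping IP among those who remain is unrelated to response, and reversal is full, the visit mean is (1-f)×E/(1-g). With E = -20%:
- f = 20%, g = 5%: 0.80 × (-20)/0.95 = -16.8
- f = 10%, g = 10%: 0.90 × (-20)/0.90 = -20.0
- f = 5%, g = 20%: 0.95 × (-20)/0.80 = -23.8

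The sign of the net shift depends on whether f exceeds g, and the documents give neither. An on-treatment mean would read E/(1-g): it removes the effect of f but not that of g.

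**The case against.** The strongest reply is that nothing is wrong with the tables. Keeping all values after stopping is a recognised treatment-policy summary, the objective does not specify on-drug efficacy, and the analysis is descriptive with no inference. That stands, as far as the validity of the all-observed tables goes. A reader might infer that they fail to measure efficacy of long-term administration; the documents do not support that. What is missing is a statement of what they measure, and a companion.

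Second, the reversal evidence is indirect. It comes from a phase 2 extension whose parent studies included heterozygous but not homozygous FH (Protocol Table 1). Its week 4 counts from extension entry, so time since the last parent dose may be longer. Here lipid therapy may change after week 12 and apheresis is allowed at any time (Protocol 6.3), so off-IP values need not return to baseline. This stands and limits the size, not the existence, of the mixing.

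Third, other planned outputs help: IP and study discontinuation tabulated separately (SAP 10.2), exposure (10.7.5), PCSK9 change by visit (10.6.2) and drug concentration profiles (10.6.3). They show that stopping occurs and may help identify who has stopped, but none ties dosing status to the lipid values in a given visit mean.

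Fourth, different conventions for safety and lipids are not in themselves an error. Agreed; the adverse event window shows only that the SAP already handles time since last dose where it chooses to.

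**Conclusion.** The gap is real and moderate. Values taken after the last dose enter the by-visit means and 15% response rates unseparated, and the planned tables cannot tell a change in drug effect from discontinuation. The size is not established: every figure in the table rests on an assumed off-IP share and an assumed degree of reversal. The primary endpoint and the sample size are untouched.

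Three stronger readings should not be drawn:
- That late-visit results will drift toward zero. Off-IP values arise only from subjects who stop IP and stay in the study; those who leave contribute nothing later, and loss of low responders acts the other way.
- That values after missed doses should also be removed. Occasional missed doses are arguably part of long-term administration. The records may not support such a rule either: Protocol 6.1.1 specifies date, time and volume on the eCRF for doses given at the site, all subjects may self-administer from week 24, and for home dosing SAP 6.1 names only a final-dose date.
- That the on-treatment summary should replace the all-observed tables or rank above them. It is restricted to subjects who stayed on drug, which is a selection of its own.

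**What to change.** In SAP 10.6.1:
1. State that the planned by-visit lipid tables include values regardless of IP discontinuation.
2. Add a supplementary by-visit on-treatment summary of the secondary lipid endpoints in the HoFH and severe FH sets. Exclude values taken after the end-of-IP date plus the longest dosing interval the protocol glossary permits for the last regimen (35 days for QM, 21 days for Q2W), capped at end of study.
3. Show the number of on-IP and off-IP values at each visit.

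The 28- and 14-day limits in SAP 6.3 are an alternative already in the plan, but they could drop end-of-study values drawn inside the permitted ±7-day window. In the example above, the week 60 panel (day 421) falls before the limit of day 435 and is kept; the week 72 panel (day 505) is left out.

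The cost is SAP wording and one extra table per set, using the end-of-IP date already defined in SAP 6.1. Design, conduct and sample size do not change. The downsides are fewer values at late visits and a mean restricted to those who stayed on drug, so neither table should be read alone. Because the cut uses the last dose only, an interruption followed by a restart stays inside the on-treatment summary; the table footnote should say so.

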# 7.2 Full Analysis Set

The full analysis set will include all subjects enrolled and dosed in this study.

8. Interim Analysis and Early Stopping Guidelines

A protocol-specified interim analysis was performed to facilitate phase 3 dose selections via an assessment of the safety, tolerability, and efficacy of 6 AMG-145-dosing regimens from the ongoing phase 2 program. There were no plans to modify or discontinue this study based on the results of the interim analysis. Also, additional analysis may be performed periodically throughout the study after parent studies are closed and individual subjects are unblinded to their lipid values.

# 9. Data Screening and Acceptance

## 9.1 General Principles

The objective of the data screening is to assess the quantity, quality and statistical characteristics of the data relative to the requirements of the planned analyses.

Statistical Analysis Plan: 20110271

Dated: 26 May 2018 Page 14 of 27

#### 9.2 Data Handling and Electronic Transfer of Data

Amgen's Clinical Data Management department will provide all data to be used in the planned analyses. This study will use the RAVE database.

All data collected in the eCRF will be extracted from RAVE. Protocol deviations will be transferred from eClinical. Final PK data for all enrolled subjects will be transferred from statistical programming to Amgen's PKDM group. Details on data transfer will be provided in the Data Transfer Plan.

## 9.3 Handling of Missing and Incomplete Data

## 9.3.1 Patterns of Missing Data

Subjects may be missing specific data points for various reasons. In general, data may be missing due to a subject's early withdrawal from study, a missed visit, or non-evaluability of a data point or an endpoint at a particular point in time. In the Data Quality Review (DQR) process, queries will be made to the sites to distinguish true missing values from other unknown values (eg, due to measurement or sample processing error). All attempts will be made to capture missing or partial data for this trial prior to the database lock for the final analysis.

The frequency and pattern of missing data for endpoints will be assessed through descriptive summaries of the measurements over time. There will be no imputation for missing data.

# 9.3.2 Missing Lipid Panel Endpoint

There will be no imputation for missing lipid panel endpoints.

#### 9.4 Detection of Bias

This study has been designed to minimize potential bias. Investigators and staff involved with this trial should remain blinded to locally obtained lipid panels until the Week 8 visit for all subjects that transition from Part B of the parent study 20110233 or other qualifying blinded parent studies into this study. This is done to avoid potential parent study unblinding.

Major protocol deviations likely to impact the analysis and interpretation of the endpoints have the potential to bias the results of the study. Important protocol deviations likely to impact the analysis and interpretation of the efficacy endpoints will be tabulated in the Clinical Study Report (CSR).

Additional sensitivity analyses may be included to assess the impact of the biases on the primary endpoint. If any sensitivity analyses are required to evaluate potential biases in the study's conclusions, then the sources of the potential biases and results of the sensitivity analyses will be documented in the CSR.

#### 9.5 Outliers

Various methods, including univariate summaries, histograms, scatterplots, box plots, and line graphs, may be used to identify outliers in key safety and efficacy variables. Extreme data points will be identified during the blinded review of the data prior to database lock. Such data points will be reviewed with clinical data management to ensure accuracy. **Unless specified otherwise, all analyses** will include outliers in the data. Sensitivity analyses may be undertaken if extreme outliers for a variable are observed.

#### 9.6 Distributional Characteristics

Statistical analyses in this study are descriptive in nature. No statistical inference is planned. So there are no statistical assumptions made for the data distribution.

Statistical Analysis Plan: 20110271

Dated: 26 May 2018 Page 16 of 27

#### 9.7 Validation of Statistical Analyses

Programs will be developed and maintained, and output will be verified in accordance with current risk-based quality control procedures.

Tables, figures and listings will be produced with validated standard macro programs where standard macros can produce the specified outputs.

The production environment for statistical analyses consists of Amgen-supported versions of statistical analysis software.

#### 10. Statistical Methods of Analysis

## 10.1 General Principles

Statistical analyses in this open label, single arm study are descriptive in nature. No statistical inference or missing value imputation is planned. Subject disposition, demographics and baseline characteristics will be summarized.

Summary statistics for continuous variables will include the number of subjects, mean, median, standard deviation or standard error, 25th percentile (Q1), 75th percentile (Q3), minimum, and maximum. For categorical variables, the frequency and percentage will be given.

Final analyses will be based on data collected from this study. Descriptions of any integrated analyses with the parent studies are out of scope for this study.

The final analysis for the study will be performed at the end of the study (defined as when the last subject has completed the assessments for week 260 or until the investigator's recommendation of discontinuation, Amgen's recommendation of discontinuation, the subject's decision to discontinue for any reason, or until an administrative decision is made to close the study). At that time, the database will be cleaned, processed and locked. All endpoints will be analyzed based on this snapshot.

For the interim analysis, subjects were summarized by the 20110233 parent rollover/non-20110233 parent rollover and assigned treatment groups in 20110233 (AMG 145 or placebo) if applicable. However, for the final analysis, subjects will be summarized based only on the apheresis status at **enrollment** when applicable described in section 6.3.

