4.1 Inclusion Criteria

4.1.1 Participated in a qualifying AMG 145 parent protocol and have a diagnosis of familial hypercholesterolemia. Subjects must not have experienced an IP treatment related serious adverse event that led to IP discontinuation during their participation in the qualifying AMG 145 parent study, or

Subjects that have not participated in a qualifying AMG 145 parent protocol must also meet all of the following inclusion criteria:

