10. STATISTICAL CONSIDERATIONS

10.1 Study Endpoints, Subsets, and Covariates

10.1.1 Primary Endpoint

Subject incidence of treatment emergent adverse events

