10.4 Planned Methods of Analysis

10.4.1 General Approach/Considerations

Statistical analyses in this open label study are descriptive in nature. No statistical inference or missing value imputation is planned. **The final analysis for the study will be performed at the end of the study (defined as when the last subject has completed the assessments for week 260 or until the investigator's recommendation of discontinuation, Amgen's recommendation of discontinuation, the subject's decision to discontinue for any reason, or until an administrative decision is made to close the study).**

Subject disposition, demographics and baseline characteristics will be summarized.

Summary statistics for continuous variables will include the number of subjects, mean, median, standard deviation or standard error, minimum, and maximum. For categorical variables, the frequency and percentage will be given.

Subjects will be summarized according to whether subject rolled over from a parent study and their treatment allocation from a parent study when applicable.

For efficacy analyses, the baseline value is defined as:

- Subjects that participated in a qualifying parent study (including 20110233) and with baseline data from the parent study: the baseline is defined as the baseline of the qualifying parent study
- Subjects not enrolling from a parent study or without baseline data from the parent study: the baseline is defined as the baseline in this study

For non-efficacy analyses, baseline values for all subjects are defined as this study baseline values.

The percent change and absolute change from baseline in laboratory based exploratory endpoints at each scheduled visit will be summarized. Summaries of vital signs, ECGs, and anti-AMG 145 antibodies will be also provided.

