#### 6.1 Study Time Points

# **Baseline**

For parent study rollover subjects, baseline is defined as the baseline of the parent study.

For non-parent study subjects, baseline is defined as the time period before the first administration of AMG 145. In particular, for non-parent apheresis subjects, if an assessment was done both pre- and post-apheresis, only the assessment made pre-apheresis will be considered baseline.

Statistical Analysis Plan: 20110271

Dated: 26 May 2018 Page 10 of 27

For hemoglobin A1c, baseline is defined as the study 20110271 baseline for all subjects, as hemoglobin A1c was not collected in study 20110233.

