# 11. Changes From Protocol-specified Analyses

The protocol specifies treatment-related adverse events will be tabulated by system organ class and preferred term for each treatment arm. This tabulation will not be included in the primary analysis. Instead treatment-related adverse events will be included in the overall adverse event summary and a tabulation of events of interest will be included.

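### The final analysis drops the protocol's split by parent-study rollover and parent treatment without declaring it, so the adverse-event tables mix prior-exposed and first-exposure subjects

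*SAP*

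**What the plan says.** Protocol 10.4.1, repeated in the synopsis, sets the grouping: "Subjects will be summarized according to whether subject rolled over from a parent study and their treatment allocation from a parent study when applicable". The primary endpoint in Protocol 10.1.1 is "Subject incidence of treatment emergent adverse events".

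SAP 10.1 reports that the interim analysis grouped subjects by 20110233 rollover status and by "assigned treatment groups in 20110233 (AMG 145 or placebo) if applicable". The same paragraph then says that "for the final analysis, subjects will be summarized based only on the apheresis status at" enrollment. SAP 6.3 carries this through: "All tables will be summarized by the following study cohorts", and the cohorts are non-apheresis and apheresis at baseline.

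SAP 11 declares one departure, which begins: "The protocol specifies treatment-related adverse events will be tabulated by system organ class and preferred term for each treatment arm". It does not mention the rollover and parent-treatment split.

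**The concern.** Subjects reach Day 1 of 20110271 with different histories. Those with no parent study, and those on placebo in a parent study, start AMG 145 here. Those on AMG 145 in a parent study do not. SAP 6.3 counts a TEAE from the first dose of IP, which SAP 6.1 defines as the first dose in the extension. For a previously treated subject, events at first exposure therefore fall outside this study's count. SAP 10.1 also puts integrated analyses with the parent studies out of scope, so this plan does not recover them.

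Rollovers also pass a filter that a new subject cannot meet. Protocol 4.1.1 states: "Subjects must not have experienced an IP treatment related serious adverse event that led to IP discontinuation" during the parent study, and 4.2.4 repeats this as an exclusion.

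The study's primary purpose is to describe safety and tolerability. If event rates differ by prior exposure, an incidence pooled over all subjects is an average over an undisclosed mix. It describes neither patients starting the drug nor patients continuing it. The protocol's split would show whether this matters. The SAP removes it from the final tables and gives no reason.

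**Working it through.** **1. Is the split really absent from the primary tables?**

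- Protocol 10.4.1: grouping by rollover status and parent allocation, with no restriction to particular tables.
- SAP 10.1 and 6.3: apheresis status only, for all tables.
- SAP 10.5.1: TEAEs, serious TEAEs and TEAEs leading to withdrawal of IP are tabulated in all subjects. The section also calls for AE tables by actual treatment arm. That has no clear meaning in a single-arm study and does not bring back parent allocation.
- SAP 10.6.1 uses the HoFH and severe FH analysis sets for the secondary endpoints, and SAP 10.4 uses them for baseline tables. SAP 10.5.1 does not specify them for TEAEs.
- SAP 11: the change is not listed.

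The split is therefore absent from the TEAE tables, and its removal is undeclared in the section meant for that.

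**2. The plan's own precision figure.** Protocol 10.2 gives 16/310 = 5.2% with a 95% interval of (0.03, 0.08). The normal approximation reproduces it:

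0.0516 ± 1.96 × √(0.0516 × 0.9484 / 310) = 0.0516 ± 0.0246 = (0.027, 0.076).

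The other two rows also reproduce, at (0.025, 0.075) for 15/300 and (0.026, 0.074) for 16/320. No stated figure is wrong; the point is structural.

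**3. Illustration of the mixing.** With s the share previously on AMG 145, p the first-exposure rate and r the rate in prior-exposed subjects:

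pooled rate = (1 − s) × p + s × r.

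Inputs from the documents:

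- N = 310 (Protocol 10.2).
- 59 planned in 20110233 (Protocol 2.2.4).
- p = 5%, borrowed from the precision table in Protocol 10.2, where it is a planning figure and not an observed rate.

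Assumptions:

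- Half to two-thirds of the 59 had AMG 145. The allocation ratio is not given.
- r = 0 to 1%.
- No prior-exposed subjects come from other qualifying parents, whose numbers are not stated.

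| AMG 145 share of the 59 | s | r = 0 | r = 1% |
|---|---|---|---|
| half | 29.5/310 = 9.5% | 4.52% | 4.62% |
| two-thirds | 39.3/310 = 12.7% | 4.37% | 4.49% |

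This gives about 4.4-4.6% against 5%. Under the same r, each further percentage point of s lowers the pooled rate by 0.04 to 0.05 percentage points, so a reader with the true share can update the result.

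The sign depends on r. If r = 5%, pooling changes nothing. If r were 7.5% (assumption) at s = 12.7%, the pooled rate would be 0.873 × 5% + 0.127 × 7.5% = 5.3%.

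**4. Precision after splitting.** Treating the 59 as the only rollovers leaves 310 − 59 = 251 subjects with no parent study. At about 5%, 13/251 = 5.2% has an approximate interval of 2.4% to 7.9%, against 2.7% to 7.6% for all 310. For the 59 rollovers, 3/59 = 5.1% has an exact interval of 1.1% to 14.2%. Dividing the 59 by parent treatment would widen it further.

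**The case against.** The change is not hidden. SAP 10.1 sets the interim and final rules next to each other, and the interim analysis did use parent status and allocation, so many early events may already have been shown by group. This stands in part. The omission from SAP 11 is a documentation gap, not concealment. However, the interim split covered 20110233 only, which leaves rollovers from other parents in the other group, and it does not supply the final tables that the protocol calls for.

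Apheresis status and disease type separate the groups to some extent. The apheresis schedule in Protocol Appendix A is headed as non-parent, and 20110233 is an HoFH study. That is fair, but it suggests that the mixing is concentrated in the non-apheresis column, and the HoFH and severe FH sets are not specified for the TEAE tables.

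Some stronger readings are tempting and should be resisted:

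- **That rollovers are selected for tolerating AMG 145.** The criterion removes only related SAEs that led to IP discontinuation. All SAEs, related or not, occurred in 2.1% of AMG 145 subjects in completed phase 2 studies (Protocol 2.2.4.4), so the group removed is probably small. Parent-placebo rollovers never took the drug, and nothing in the documents says that poor tolerators decline to roll over.
- **That 59/310 = 19% of subjects are pre-exposed.** That count includes parent-placebo subjects, who are on first exposure here.
- **That overall TEAE incidence is materially understated.** It was already 57% on AMG 145 in completed phase 2 studies, and here it accrues over up to 260 weeks. The first weeks matter far less to it than to an uncommon early-onset event.
- **That the HbA1c baseline or the antibody count is an error.** Protocol 10.4.1 sets the 20110271 baseline for all non-efficacy analyses, and SAP 6.1 gives the reason for HbA1c: "as hemoglobin A1c was not collected in study 20110233". Counting antibodies at any time follows Protocol 10.4.2.3.

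**Conclusion.** The point holds as an undeclared departure from the protocol that affects the primary endpoint tables. The textual discrepancy is certain. That pooled TEAE incidence mixes prior-exposed and first-exposure subjects follows directly from the TEAE and first-dose definitions.

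The size and direction of any distortion are not established. The 4.4-4.6% range is an illustration for a single uncommon event. It rests on an assumed parent allocation, an assumed 0-1% rate in prior-exposed subjects, and a 5% rate taken from a precision table. The whole range lies inside the interval of 3% to 8% that the plan prints for 310 subjects. It does not show that the reported safety profile will be too favourable.

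A reader might also infer that the headline incidence should come from subjects new to AMG 145. The documents do not support that: the primary objective concerns long-term administration in the whole enrolled population, so the choice of headline is a preference.

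**What to change.** In SAP 10.1, 6.3 and 10.5.1, add the protocol's grouping as columns beside the apheresis cohorts: no parent study, parent placebo, and parent AMG 145, covering every qualifying parent study and not only 20110233. Apply it to TEAEs, serious TEAEs and TEAEs leading to withdrawal of IP. The all-subjects column can stay.

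If the split is dropped for any table, list that in SAP 11 with the reason.

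The cost is SAP wording and extra table columns. Allocation in 20110233 was already used at the interim; allocation from other parents would need to be brought in. The statistical downside is smaller denominators: little is lost for subjects with no parent study, but the rollover columns will be imprecise and should be read descriptively.
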